6.0 DETERMINATION OF SAMPLE SIZE

As no formal hypothesis testing is performed for the primary endpoint, the purpose of sample size estimation is to determine the adequate sample size needed to provide a precise estimate for the response rate (GAS Score ≥ 50) with 95% CIs.

Conservatively estimating that 50% of subjects will be responders (GAS ≥ 50) and that 100 subjects will complete the study, CIs will be ± 0.098 around the point estimate (proportion of responders).

7.0 METHODS OF ANALYSIS AND PRESENTATION

7.1 General Principles

This is an open-label study with a single treatment regimen and all comparisons are made to the conditions prior to the subject being switched to vortioxetine.

Baseline values are defined as the last observed value before the first dose of study switch medication.

All statistical analyses will be conducted using SAS® Version 9.2, or higher.

All confidence intervals, statistical tests, and resulting P-values will be reported as 2-sided and will be assessed at $\alpha=0.05$ significance level unless otherwise stated. P-values will be rounded to 3 decimal places prior to assessment of statistical significance.

Means and medians will be presented to 1 more decimal place than the recorded data. The standard deviations (SDs) will be presented to 2 more decimal places than the recorded data. Confidence intervals about a parameter estimate will be presented using the same number of decimal places as the parameter estimate.

Where appropriate, variables will be summarized descriptively by study visit. For the categorical variables, the count and proportions of each possible value will be tabulated. The denominator for the proportion will be based on the number of subjects who provided non-missing responses for the categorical variable. For continuous variables, the numbers of subjects with non-missing values, mean, median, SD, minimum, and maximum values will be tabulated.

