13.1.1 Analysis Sets

In this study, 3 kinds of analysis sets are defined: full analysis set (FAS), per protocol set (PPS), and safety analysis set. The definition of each analysis set will be described in the Handling Rules for Analysis Data.

The FAS, used for primary effectiveness analysis, will include all subjects who were enrolled in the treatment period and received at least 1 dose of the study drug and completed at least 1 GAS assessment post-Baseline. In FAS effectiveness summaries, subjects will be considered as vortioxetine treated no matter what dose levels were received during the study.

A PPS will include all FAS subjects who had no major protocol violations. Subjects to be excluded from the PPS, whether due to protocol violations or noncompliance to the dosing prescribed by the treating physician, will be identified in the minutes of the subject evaluability assessment.

The Safety Set will include all subjects who were enrolled and received at least 1 dose of study medication. In safety summaries, all subjects will be analyzed as vortioxetine-treated.

The sponsor will verify the validity of the definitions of the analysis sets as well as the rules for handling data, with consulting a medical expert as needed. If necessary, the Handling Rules for Analysis Data will be supplemented with new handling rules that were not discussed at the planning stage. The Handling Rules for Analysis Data must be finalized prior to database lock.

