7.1.2 Definition of Visit Window

The window definitions as stated will be applicable for all the summaries where study visit data is presented and where study visit data are compared with baseline data. The window conventions for safety and efficacy parameters are consecutive; that is, the lower or upper bound of the windows is the midpoint between 2 consecutive study visits.

One or more results for a parameter may be obtained in a visit window. In such an event, the result with the closest date to the scheduled visit date will be used. In the event of 2 observations within a given visit window being equidistant to the scheduled visit date, the later observation will be used.

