7.2 Analysis Sets

In this study, 3 kinds of analysis sets are defined: full analysis set (FAS), per protocol set (PPS) and safety analysis set.

The FAS, used for primary effectiveness analysis, will include all subjects who were enrolled in the treatment period and received at least 1 dose of the study drug and completed at least 1 GAS assessment post-Baseline. In FAS effectiveness summaries, subjects will be considered as vortioxetine-treated no matter what dose levels were received during the study.

A PPS will include all FAS subjects who had no major protocol violations. Subjects to be excluded from the PPS, whether due to protocol violations or noncompliance to the dosing prescribed by the treating physician, will be identified in the minutes of the subject evaluability assessment.

The Safety Analysis Set will include all subjects who were enrolled and received at least 1 dose of study medication. In safety summaries, all subjects will be analyzed as vortioxetine-treated.

The sponsor will verify the validity of the definitions of the analysis sets as well as the rules for handling data, with consulting a medical expert as needed. If necessary, the Handling Rules for Analysis Data will be supplemented with new handling rules that were not discussed at the planning stage. The Handling Rules for Analysis Data must be finalized prior to database lock.

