7.8 Efficacy Analysis

The primary objective of the study is to determine the effectiveness of treatment with vortioxetine on subject goal achievement after changing antidepressant medication for treatment of MDD. The primary endpoint is the proportion of subjects who changed to treatment with vortioxetine and achieved their individually identified goals as demonstrated by an outcome GAS Score of ≥ 50 at Week 12. This proportion will be summarized at Week 12. All efficacy analyses will use the FAS.

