7.8.1 Primary Efficacy Endpoint

The GAS is a tool to measure the progress each subject has towards achieving their individualized goals. While the outcome measure is unique to each subject, standardized scoring is applied to allow for statistical analysis.

The GAS allows for 1 of 2 types of goals to be set:

- (1) Subject defined goals allow a “subject’s chief complaint” approach taken towards establishing the goal, with no specific limitations set for the type or focus of the goal, beyond requiring that it meets the basic standards of measurability, equidistance, and difficulty.
- (2) Domain-defined goals are more structured in nature, presenting the subject with an array of broadly defined domains and more specific subdomains. After selecting an appropriate domain and (where applicable) subdomain, the clinician will work with the subject to establish a specific goal that fits within the selected category.

For GAS, a total of 3 goals will be selected, 1 subject defined and 2 from pre-defined domain categories. A 5-point rating scale will then be applied to each of the 3 goals. A semi-structured interview will be conducted with each subject to conduct goal-setting at the outset of the study.

Another evaluation will take place at Week 6 and Week 12/End of Study visits or at Early Termination Visit (as applicable) to determine the level of progress at that time, with assignment of appropriate scores. It takes subjects approximately 45 minutes to complete the GAS.

Calculating the Overall GAS

The goals identified are incorporated into the single GAS score by applying a formula:

$$\text{Overall GAS} = 50 + \frac{10 * \sum(w_i x_i)}{\sqrt{(1-\rho) \sum w_i^2 + \rho(\sum w_i)^2}}$$

Where:

w_i = the weight assigned to the i th goal (if equal weights, $w_i = 1$)

x_i = the numerical value achieved (between -2 and +2)

ρ = the expected correlation of the goal scales

(For practical purposes, most commonly approximates to $\rho=0.3$)

For this study, a choice of weight is based on importance of the goal. Weight is 1, 2, and 3 for least important, moderately important and most important goals, respectively. The expected correlation of 0.3 was selected for this study.

The GAS will be summarized for both Week 6 and Week 12 using both percents of response and as a continuous score. An overall GAS score greater than 50 is considered as a response.

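### Read by its general defaults, the SAP makes the primary Week 12 GAS responder rate an observed-case rate, and no visible rule says how an Early Termination or missing score counts

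*SAP*

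**What the plan says.** **Endpoint and population.** SAP 7.8 takes the responder proportion at Week 12 as the primary result and adds that "All efficacy analyses will use the FAS". SAP 7.8.1 says: "The GAS will be summarized for both Week 6 and Week 12 using both percents of response and as a continuous score". Under SAP 7.2 an FAS subject must have "received at least 1 dose of the study drug and completed at least 1 GAS assessment post-Baseline". Protocol 13.1.1 fixes the same set for the primary analysis: "The FAS, used for primary effectiveness analysis, will include all subjects who were enrolled in the treatment period".

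**Denominator.** SAP 7.8 and 7.8.1 state none. The only rule is the general one in SAP 7.1: "The denominator for the proportion will be based on the number of subjects who provided non-missing responses for the categorical variable".

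**Assigning scores to visits.** SAP 7.1.2 covers efficacy as well as safety data. Windows are consecutive, and "the lower or upper bound of the windows is the midpoint between 2 consecutive study visits". If a window holds several results, "the result with the closest date to the scheduled visit date will be used". The section prints no days and does not say whether the visits meant are all scheduled visits or only those at which the parameter is measured.

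**Early Termination.** SAP 7.8.1 has the GAS rated at Week 6 and at Week 12 or ET. Protocol 7.5 asks sites to try to complete the ET procedures after withdrawal. Protocol 9.3.5 treats Week 12 and ET as alternative forms of the Final Visit, and Protocol Appendix A puts them in one column. These are rules about visits and data collection. None says how an ET score enters the analysis.

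**Elsewhere.** Both documents refer to a separate document, the Handling Rules for Analysis Data, which is not supplied. The per-protocol set is defined but given no efficacy role. The visible text names no sensitivity analysis of the primary rate.

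**The concern.** A subject can qualify for the FAS on a Week 6 or ET score and have nothing in the Week 12 window. Under the 7.1 default that subject leaves the primary proportion altogether, so the reported rate describes subjects who stayed in the study to the end or nearly so.

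The study has one arm and reports an absolute rate with a confidence interval, so there is no comparator in which an effect of dropout could cancel. Adverse events and lack of effectiveness are listed withdrawal reasons (Protocol 7.4), and withdrawn subjects are not replaced (Protocol 7.5). If those who leave reach their goals less often than those who stay, the rate comes out too high.

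Two programmers could also follow the same text and obtain different primary rates, one placing ET scores by date and the other treating ET as the Week 12 record. The SAP's futility look uses a 50% responder rate as its reference (SAP 7.10), so shifts of a few points near that value affect how the result is read.

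**Working it through.** **1. The plan's own figure.** Both documents assume 50% responders and 100 completers (Protocol 13.3, SAP 6.0). The half-width is 1.96 × √(0.5 × 0.5 / 100) = 0.098, as stated. With all 120 enrolled it would be 0.0895, so the planned precision rests on completers.

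**2. The Week 12 window.** Scheduled days in Protocol Appendix A are 1, 15, 29, 43, 64, 85 and 113.
- All visits: the midpoints are 8, 22, 36, 53.5, 74.5 and 99. Week 12 starts at (64 + 85)/2 = 74.5, so at Day 75.
- GAS visits only (Days 1, 43, 85): the midpoints are 22 and 64. Week 12 starts at (43 + 85)/2 = 64. Day 64 itself is a tie that 7.1.2 does not assign.

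**3. Two examples.** Each subject has a Week 6 GAS on Day 43 and then an ET GAS.
- ET on Day 60: with all-visit windows the score falls in Week 9, where no GAS summary is planned. With GAS-visit windows it falls in Week 6, where the Day 43 score is 0 days from target against 17 and is kept. Either way the subject is in the FAS but not in the Week 12 rate.
- ET on Day 70: with all-visit windows the score is in Week 9 and is left out. With GAS-visit windows it counts at Week 12. The unstated choice of visits decides the matter.

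**4. Size.** From the plan: 120 enrolled, 100 completing, so 20 non-completers. Assumed: only the 100 completers have a Week 12 GAS, k of the 20 are in the FAS (not given; range 0 to 20), and a fraction q of those k respond. With observed rate p, the rate over all FAS subjects is (100p + kq)/(100 + k), and

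overshoot = p − (100p + kq)/(100 + k) = (p − q) × k/(100 + k).

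At p = 0.50:

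| k | FAS rate if q = 0 | Overshoot, q = 0 | Overshoot, q = 0.25 | Overshoot, q = 0.50 |
|---|---|---|---|---|
| 0 | 50/100 = 50.0% | 0 | 0 | 0 |
| 5 | 50/105 = 47.6% | 2.4 points | 1.2 | 0 |
| 10 | 50/110 = 45.5% | 4.5 | 2.3 | 0 |
| 15 | 50/115 = 43.5% | 6.5 | 3.3 | 0 |
| 20 | 50/120 = 41.7% | 8.3 | 4.2 | 0 |

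The normal-approximation 95% intervals are 40.2 to 59.8% for 50/100 and 32.8 to 50.5% for 50/120. If all 120 enrolled are treated, the last row is also the all-treated rate with missing counted as non-response.

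**5. Dependence on the assumptions.** With q = 0 and p = 0.30 the overshoot is 2.7 points (k = 10) or 5.0 (k = 20). With p = 0.70 it is 6.4 or 11.7. It shrinks if some ET scores fall in the Week 12 window. It changes sign if q exceeds p: were all 20 to respond, the rate would be 70/120 = 58.3%, and the observed-case figure would be too low by 8.3 points.

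**The case against.** The strongest reply is that the plan may already intend the ET score to be the final value. Appendix A has one column for Week 12 and ET, Protocol 9.3.5 makes either one the Final Visit, and the GAS is scored at both. On that reading most withdrawn subjects in the FAS would contribute a result, and the rate would not be close to a completer rate. This stands as a reasonable reading. It does not settle the matter, because the only analysis rule on timing, SAP 7.1.2, assigns scores by date and points the other way.

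Second, the 7.1 denominator sentence sits in a general paragraph on descriptive summaries by visit, qualified as applying where suitable. That the primary rate is observed-case is therefore an inference from a default and is nowhere stated for this endpoint. That is right, but no other denominator is given. SAP 7.10 projects the responder rate to 120 subjects, which hints at a fuller denominator, but it concerns the interim look and sets no rule for the final analysis.

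Third, the Handling Rules may contain the answer, and some analysis text is blacked out. Any statement that a rule is absent is therefore limited to the visible protocol and SAP. Protocol 13.1 nevertheless gives the SAP the task of defining analysis variables and methods.

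Fourth, non-responder counting has its own fault. If out-of-window ET scores are ignored, the Day 70 subject could meet the goals and still be labelled a non-responder under all-visit windows. That objection is sound, so the ET rule must be stated together with the denominator.

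**Conclusion.** The point holds as a gap with a default behind it. If the SAP is followed as written, the primary rate is observed-case, and FAS subjects whose last GAS precedes about Day 64 or Day 75 drop out of it. Whether the ET score was meant to replace the Week 12 score is left open.

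On the plan's figures and a 50% observed rate, the overstatement is 0 if the k subjects respond like completers. If none respond, it is 4.5 points at k = 10 and at most 8.3 at k = 20, against a planned half-width of 9.8 points. Both k and the response among those subjects are assumptions.

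A reader might infer that the trial's rate will be inflated by about 8 points. The documents do not support that: it needs all 20 non-completers in the FAS, none with a score in the Week 12 window and none responding, and nothing in the documents shows how withdrawn subjects respond. A reader might also infer that the sponsor chose to discard ET scores. The text shows no such decision. The gap is worth closing because the data are already to be collected and the result depends on rules that can be written in a few lines.

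**What to change.** - **SAP 7.8.1:** make all FAS subjects the denominator of the primary Week 12 rate, in place of the 7.1 non-missing default, and count those with no usable GAS as non-responders. State whether an ET GAS outside the Week 12 window counts as the final value.
- **Named sensitivity analyses:** the observed-case rate, the rate under the other ET rule, and the rate over all treated subjects with missing counted as non-response.
- **SAP 7.1.2:** state which visits define the windows, print them in days, and assign the midpoint day.
- **Handling Rules:** if they already settle any of this, carry the rule into the SAP.

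The cost is SAP wording and programming, with no new data. The FAS remains the primary set, as Protocol 13.1.1 requires. An all-treated primary denominator would need that section amended or the change documented, so it is proposed only as a sensitivity analysis. The downside is that the headline rate may be lower and may understate success if some withdrawn subjects met their goals; the sensitivity analyses would show by how much.

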7.1.1 Definition of Study Days

Study Day 1 is defined as the date on which a subject is administered their first dose of the vortioxetine medication. Other study days are defined relative to the Study Day 1 with Day 1 being Study Day 1 and Day -1 being the day prior to Study Day 1.

7.1.2 Definition of Visit Window

The window definitions as stated will be applicable for all the summaries where study visit data is presented and where study visit data are compared with baseline data. The window conventions for safety and efficacy parameters are consecutive; that is, the lower or upper bound of the windows is the midpoint between 2 consecutive study visits.

One or more results for a parameter may be obtained in a visit window. In such an event, the result with the closest date to the scheduled visit date will be used. In the event of 2 observations within a given visit window being equidistant to the scheduled visit date, the later observation will be used.

7.2 Analysis Sets

In this study, 3 kinds of analysis sets are defined: full analysis set (FAS), per protocol set (PPS) and safety analysis set.

The FAS, used for primary effectiveness analysis, will include all subjects who were enrolled in the treatment period and received at least 1 dose of the study drug and completed at least 1 GAS assessment post-Baseline. In FAS effectiveness summaries, subjects will be considered as vortioxetine-treated no matter what dose levels were received during the study.

A PPS will include all FAS subjects who had no major protocol violations. Subjects to be excluded from the PPS, whether due to protocol violations or noncompliance to the dosing prescribed by the treating physician, will be identified in the minutes of the subject evaluability assessment.

The Safety Analysis Set will include all subjects who were enrolled and received at least 1 dose of study medication. In safety summaries, all subjects will be analyzed as vortioxetine-treated.

The sponsor will verify the validity of the definitions of the analysis sets as well as the rules for handling data, with consulting a medical expert as needed. If necessary, the Handling Rules for Analysis Data will be supplemented with new handling rules that were not discussed at the planning stage. The Handling Rules for Analysis Data must be finalized prior to database lock.

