13.0 STATISTICAL METHODS

13.1 Statistical and Analytical Plans

A statistical analysis plan will be prepared and finalized prior to database lock. This document will provide further details regarding the definition of analysis variables and analysis methodology to address all study objectives.

A data review will be conducted prior to database lock. This review will assess the accuracy and completeness of the study database, subject evaluability, and appropriateness of the planned statistical methods.

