7.10 Interim Analysis

The responder rate based on GAS score ≥ 50 will be calculated. The conditional probability of a responder rate of less than 50% at 120 subjects will be assessed; that is, using the data /trend of 60 patients at the interim look, the probability of (responder rate $< 50\%$) at the end of study (i.e., 120 subjects) will be calculated.

In addition, the change in PHQ9 and PDQ will be evaluated for internal decision making.

The report to be prepared for the interim analysis should include the tables for the following: demographics, disposition, GAS Response percents, GAS change from baseline, PHQ-9, and PDQ-D.

The end of the study will be the date of the last safety follow-up visit of the last subject based either on the first 60 completed subjects or the final 120 completed subjects.

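### Handling rules that bear on the primary responder rate can be added until database lock, which may fall after the open-label interim rate has been reported

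*SAP*

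**What the plan says.** **Deadline.** Protocol 13.1.1, repeated in SAP 7.2, says: "The Handling Rules for Analysis Data must be finalized prior to database lock". Protocol 13.1 gives the SAP the same deadline: "A statistical analysis plan will be prepared and finalized prior to database lock". It also provides for a data review before lock that covers subject evaluability and whether the planned methods are appropriate.

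**Scope.** According to Protocol 13.1.1, "The definition of each analysis set will be described in the Handling Rules for Analysis Data". SAP 7.2 adds: "The sponsor will verify the validity of the definitions of the analysis sets as well as the rules for handling data". If necessary, the rules may be "supplemented with new handling rules that were not discussed at the planning stage". SAP 7.11, where changes to the plan would be recorded, holds only a placeholder.

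**Interim.** SAP 7.10 states: "The report to be prepared for the interim analysis should include the tables for the following: demographics, disposition, GAS Response percents". The list goes on to GAS change, PHQ-9 and PDQ-D, and changes in PHQ-9 and PDQ are to inform internal decisions. Protocol 13.2 and SAP 4.4 say the futility analysis will be done. Protocol 2.0 and 6.1 say it may be done.

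**Masking and oversight.** SAP 7.1 says: "This is an open-label study with a single treatment regimen". Protocol 11.0 states that no steering, safety monitoring or endpoint committee is used. Neither document limits who receives the interim report.

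**The concern.** Finalizing the rules before lock protects a trial mainly because, until then, nobody choosing them can see the treatment comparison. Here there is no allocation to hide. Any tabulation of GAS scores is already an estimate of the primary result, and the plan calls for one about halfway through. A rule added between that report and lock could be chosen, knowingly or not, with the responder rate in view.

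The primary result is a single proportion with no comparator. A rule that favours responders is not offset by the same rule acting on a control arm, so it passes straight into the reported rate. What is at stake is bias in that estimate and in how it reads against the 50% mark used at the interim.

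**Working it through.** **Inputs.** About 120 enrolled (Protocol 6.1, SAP 4.4). 100 completers, 50% responders and a 95% half-width of 0.098 (Protocol 13.3, SAP 6.0). Interim at about 60 completers (Protocol 13.2, SAP 4.4). Goal weights 1, 2 and 3, with scores from -2 to +2 (SAP 7.8.1).

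**1. The plan's precision figure.** Half-width = 1.96 × √(p(1 − p)/n) = 1.96 × √(0.5 × 0.5/100) = 0.098. It reproduces. At the interim, with n = 60, it is 1.96 × √(0.25/60) = 0.127.

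**2. How much the interim reveals.** If 60 of a final 120 subjects are in hand, the interim and final rates correlate at √(60/120) = 0.71. SAP 7.10 asks for the probability that the final rate is below 50% if the interim trend continues. With r responders in 60, that is P(X ≤ 59 − r) for X ~ Binomial(60, r/60):

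| Interim | P(final rate < 50%) |
|---|---|
| 27/60 | 0.92 |
| 30/60 | 0.45 |
| 33/60 | 0.05 |

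A reader of the interim report would therefore have a fair idea of where the final rate will fall.

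**3. What is already fixed.**
- The full analysis set (FAS): enrolled, dosed at least once, with a GAS assessment after Baseline (SAP 7.2, Protocol 13.1.1). SAP 7.8 applies it to every efficacy analysis.
- Visit windows: midpoint boundaries, nearest result, later result on a tie (SAP 7.1.2).
- Default denominator: subjects with non-missing responses (SAP 7.1).
- Per-protocol exclusions are left open (they "will be identified in the minutes of the subject evaluability assessment"), but no efficacy analysis uses that set.

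**4. What is not settled for the primary proportion.**
- *Cut-off.* SAP 7.8.1 spells out a score greater than 50. SAP 5.1, 6.0, 7.8 and 7.10 use 50 or more. A score of exactly 50 requires x₁ + 2x₂ + 3x₃ = 0, which holds for 9 of the 5³ = 125 score patterns (7.2%). This counts patterns; it is not an expected share of subjects.
- *Early-termination GAS.* It is collected (SAP 7.8.1), but its status as a Week 12 value is not stated. The general window rule does not fully settle this. The lower bound for Week 12 is Day (43 + 85)/2 = 64 if the preceding GAS visit is used, or Day (64 + 85)/2 = 74.5 if the Week 9 telephone visit is used.
- *FAS subjects without a Week 12 GAS.* A Week 6 assessment is enough to enter the FAS. Beyond the general denominator, no rule is given.

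**5. Size, starting from 50/100.**

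| Change | Rate | Shift (points) |
|---|---|---|
| One subject's responder status flipped | 51/100 = 51.0% | 1.0 |
| One non-responder excluded | 50/99 = 50.5% | 0.5 |
| Ten non-responders excluded | 50/90 = 55.6% | 5.6 |
| Seventeen non-responders excluded | 50/83 = 60.2% | 10.2 |

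The planned half-width is 9.8 points. Sixteen such exclusions give 50/84 = 59.5%, a shift of 9.5 points, so it takes 17 exclusions in one direction to pass it.

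For subjects without a Week 12 GAS, assume that 10 of the 120 − 100 = 20 non-completers enter the FAS. The non-missing denominator leaves the rate at 50.0%. Counting all ten as non-responders gives 50/110 = 45.5%, and counting all ten as responders gives 60/110 = 54.5%. These are bounds under an assumed count.

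**The case against.** The strongest reply is that most of what decides the primary rate is already written. FAS membership is objective, windows and denominator are stated, and the discretionary exclusions belong to a set that no efficacy analysis uses. All of that stands, and it rules out several stronger readings.

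- A reader might infer that deciding who is evaluable could reshape the primary result. Only a change to the FAS definition itself could do so.
- A reader might infer that windowing is wholly open. A general rule exists; the gap is the status of an early-termination value.
- A reader might take each reclassified subject as worth a full point, so that ten would match the half-width. That holds only when responder status flips and the denominator stays fixed. Ten exclusions of non-responders move the rate 5.6 points.
- A reader might quote a range of 41.7% (50/120) to 58.3% (70/120) for missing data. That requires all 20 non-completers to enter the FAS and to be counted all one way, against the stated denominator.
- A reader might conclude that rules were in fact fitted to results, or that an error rate is inflated. The documents permit late rules but show none being made, and the primary endpoint has no formal test.

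The timing is also partly conditional. The interim is optional in two places, and its recipients are not named. The SAP speaks of it in the future tense, so the SAP itself may have been signed earlier; the text available does not show its date or the content of the Handling Rules. If the interim were skipped, outcomes would still be visible before lock.

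None of this answers the remaining point: the stated deadline is lock, not the interim, and choices that enter the primary proportion are unsettled.

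**Conclusion.** The concern holds in limited form. The plan lets handling rules be added, and analysis-set definitions be checked for validity, up to a deadline that can fall after an interim responder rate has been reported, with no described safeguard. The exposure is confined to changes to the rules already stated and to three open choices: the cut-off, early-termination GAS, and FAS subjects without a Week 12 GAS.

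Its plausible size is a few points: 1 per flipped responder status, about 0.5 per excluded non-responder, and 5.6 for ten exclusions, against a half-width of 9.8. These figures assume the plan's own 100 completers and 50 responders. The number of subjects that a late rule would affect is not known from the documents. The consequence is possible bias in a descriptive estimate, which justifies a change of timing but does not invalidate the design.

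**What to change.** Finalize and date the SAP and the Handling Rules before the interim data cut. Settle in them:

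- one responder cut-off, used in every section;
- whether, and within what days, an early-termination GAS counts as Week 12;
- how FAS subjects without a Week 12 GAS enter the numerator and denominator.

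Replace the permission to supplement the rules until lock with this: any later addition is dated, logged with its reason, and reported as a labelled sensitivity analysis beside the primary result under the pre-interim rules. State who receives the interim report, and make the wording on whether the interim takes place the same throughout.

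The cost is an earlier sign-off. Sample size and the 0.098 half-width do not change. The downside is that unforeseen data problems must be handled outside the primary analysis. Because outcomes are visible as they accrue, the change reduces result-informed choices but cannot eliminate them.
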